8.8. Pharmacokinetic Assessment

During the Sentinel Phase blood samples for assessment of TTP399 plasma concentrations will be collected concurrent to the MMTTs according to the visits shown in the Section 8.6.4 and Figure 5.

During Part 1 blood samples for assessment of TTP399 plasma concentrations will be collected at Week 0/Day 1, Week 2, 4, 6 and 8 and 12. At Week 0 the sample should be collected prior to dosing.

During Part 2 blood samples for assessment of TTP399 plasma concentrations will be collected prior to dosing according to the Schedule of events at Week 0, Week 2, Week 6, and Week 12 and ET, if applicable.

The date/time of the blood draw and the date/time of the last dose of study medication prior to the blood draw should be captured on the EDC.

Specific details regarding PK collection, processing, and shipment will be provided in the laboratory manual.

Samples will be analyzed for TTP399 concentrations using a previously developed and validated bioanalytical method. Samples may also be analyzed for TTP399 metabolite concentrations at the Sponsor's discretion. Samples will be kept until completion of the clinical study report.

8.9. Pharmacodynamic*MMTT Panel (Sentinels only)

In addition to the single sampling of glycemic markers (HbA1c, fructosamine, and 1,5 AG) at study visits, blood samples for pharmacodynamics will be collected prior to dosing and

during MMTT according to the times listed for in the Section 8.6.4 and Figure 5 (Sentinels).

Specific details regarding collection, processing, and shipment will be provided in the laboratory manual.

Samples will be kept until completion of the clinical study report.

8.10. Blood Sampling: Plasma Storage and Retention

A 4 mL blood sample will be collected for potential future analysis of plasma biomarkers (non-genomic). Sample will be collected according to the SCHEDULE OF ACTIVITIES (Sentinels) and at Week 0 and Week 12 or Early Termination (if applicable) for Parts 1 and 2. Specific details regarding retention sample collection, processing, and shipment will be provided in the laboratory manual.

A separate consent form may be provided for this voluntary sampling if not already included in the IRB approved study protocol consent form.

[figure not shown]
8.11. Management of Patients' Glycemic Control and Insulin Dose Adjustments

Patients will be counseled on identification and management of hypoglycemia and hyperglycemia. Glucose levels will be monitored using unblinded continuous glucose monitoring (if patients already have CGM) and self-monitoring of blood glucose using glucometers if unblinded CGM glucose values are not available. **Sentinel** patients are required to have a good hypoglycemic awareness and live with someone who has a good hypoglycemia awareness.

Parts 1 and 2, only

Prior to the placebo run-in period, the PI or designee will determine if the patient's basal insulin dose needs to be optimized to meet the fasting/pre-meal glucose target generally from 80-130mg/dL. If the PI determines that basal insulin dose adjustment is needed, the PI or designee, in collaboration with the patient, will optimize the basal insulin dose for up to 3 weeks prior to the placebo run-in period. If basal insulin dosing is adequate, the patient will move directly into the placebo-run in period. (See Figure 6 below).

Figure 6: Decision Flow Chart for Patient Visits Prior to Randomization

*Adjust basal insulin to target fasting/pre-meal glucose levels generally between 80-130 mg/dL

The PI or designee will use the following guidance in combination with the recent glucose data to instruct the patient on insulin adjustments needed.

BASAL INSULIN DOSE ADJUSTMENT PERIOD (up to 3 weeks before Week -2)

The PI or designee will review the past 14 days of CGM data (Part 1) or fasting/pre-meal glucose levels for the past 7 days using either CGM or glucometer data (Part 2) and determine if a basal insulin dose adjustment period is needed.

If basal insulin adjustments are needed, the basal rate should be assessed and adjusted to target fasting/pre-meal glucose levels generally between 80-130 mg/dL

If Low Blood Glucose: Make immediate insulin adjustment.

If Elevated Blood Glucose: Verify trends 2–3 days before adjusting insulin.

DURING PLACEBO RUN-IN PERIOD (2 weeks prior to randomization)

Do not make insulin adjustments except in response to safety concerns.

Record in the EDC:

- CSII: basal rate, Active Insulin Time and type of Pump, ICF and ICR
- MDI: basal insulin dosing information, ICR and ISF

DURING DOUBLE-BLIND PERIOD:**First day of dosing (Week0/Day 1):**

Reduce bolus insulin:

INCREASE insulin to carb ratio (ICR, g/U) by 1-3 g/U (10-30%, usually 20%), e.g., if the ICR is 10g/U during run-in period increase the ICR to 11 or 13g/U, usually 12g/U.

And

INCREASE insulin sensitivity factor (ISF) by 10-30%, usually 20%, e.g. if the ISF is 40g/U during run-in period increase the ISF to 44-52% or, usually 48g/U.

Record in the EDC:

- CSII: basal rate, active insulin time, ICF and ICR
- MDI: basal insulin dosing information, ICR and ISF

During the first two weeks of dosing:

Adjust insulin to the following glycemic targets:

- Fasting/pre-meal: 80-130 mg/dL
- Post-meal peak: < 180 mg/dL (post-meal peak < 200mg/dL may be acceptable target at the PI's discretion)

If Low Blood Glucose: Make immediate insulin adjustment.

If Elevated Blood Glucose: Verify trends 2–3 days before adjusting insulin.

The adjustment of bolus insulin should be accomplished by **adjusting ICR and ISF**

Record any adjustments in the EDC:

- CSII: basal rate, active insulin time, ICF and ICR
- MDI: basal insulin dosing information, ICR and ISF

After two weeks of dosing:

Adjust insulin to the following glycemic targets:

- Fasting/pre-meal: 80-130 mg/dL
- Post-meal peak: < 180 mg/dL (post-meal peak < 200mg/dL may be acceptable target at the PI's discretion)

If Low Blood Glucose: Make immediate insulin adjustment.

If Elevated Blood Glucose: Verify trends during patient calls and visits before adjusting insulin.

The adjustment of bolus insulin should be accomplished by **adjusting ICR and ISF**

Record any adjustments in the EDC:

- CSII: basal rate, active insulin time, ICF and ICR
- MDI: basal insulin dosing information, ICR and ISF

8.12. Diabetes Treatment Satisfaction Questionnaires

The Diabetes Treatment Satisfaction Questionnaire status version (DTSQs) will be completed at the Screening Visit.

The Diabetes Treatment Satisfaction Questionnaire status version (DTSQs) and the Diabetes Treatment Satisfaction Questionnaire change version DTSQc will be completed at the Week 12 visit.

8.13. Quality of Life (QOL) Question

At Week 12, the patient should be asked to respond to the following QOL question with one of the answers below. The answer will be entered in the EDC.

Question: "How is your quality of life relative to study start?"

Answers (choose one): markedly worse, moderately slightly worse, no change, slightly improved, moderately improved, markedly improved.

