10. DATA ANALYSIS / STATISTICAL METHODS

The statistical considerations summarized in the following subsection outline the plan for data analysis of this study. A Statistical Analysis Plan (SAP) will be finalized prior to unblinding the data from the study. The SAP will supersede the protocol for analyses. Any deviations from the planned analyses will be described and justified in the final integrated

study report. The analysis plans for this study will reflect sound methodologies appropriate for an adaptive study.

Continuous variables will be presented showing number of observations available, mean, median, minimum, maximum, 1st and 3rd quartiles, and standard deviations (or standard errors, depending on the variable) by visit. Categorical variables will be presented showing frequencies and percentages by visit.

All tests will be 2-sided and use an overall study-wise $\alpha = 0.05$ unless otherwise stated. SAS Version 9.1 or later will be used. Medical dictionary for Regulatory Activities (MedDRA) Version 16.0 or later will be used for coding adverse events. Medications will be coded using WHO Drug Dictionary (WHODD) Version March 2009 or later.

This study is planned using FDA guidance *Adaptive Design for Clinical Trials for Drugs and Biologics* (draft guidance, February 2010).

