- H_{15} : The mean change in time in hypoglycemia using 54 mg/dl as the threshold from baseline to Week 12 for the group treated with 800 mg TTP399 is not equal to that of the placebo group.

Conditional Fourth Statistical Evaluation:

- **Evaluation 7:**

Superiority on Quality of life Likert scale score is evaluated:

- H_{06} : The mean score for the single-item Likert scale for overall improvement in quality of life at Week 12 for the group treated with 800 mg TTP399 is equal to that of the placebo group.
- H_{16} : The mean score for the single-item Likert scale for overall improvement in quality of life at Week 12 for the group treated with 800 mg TTP399 is not equal to that of the placebo group.

3 Estimand Specification

This SAP is constructed to conform to regulatory guidance. In particular, this section is included as recommended by ICH E9 (R1) Addendum on estimands and sensitivity analysis in clinical trials to the guideline on statistical principles for clinical trials (30 August 2017).

In accordance with ICH E9 Addendum, the specification of the estimand is included in this SAP with the 4 attributes detailed in ICH E9 Addendum, Section A.3.1:

A. The Population, that is, the patients targeted by the scientific question:

For this study, the population consists of subjects with type 1 diabetes who meet eligibility requirements for the study, have qualified through the basal insulin-optimization period (if needed) and the placebo run-in period, receive double-blind medication, and have at least one valid post-baseline measure of HbA1c.

B. The variable (or endpoint) to be obtained for each patient, that is required to address the scientific question:

For this study, the primary endpoint is HbA1c with co-primary importance on treatment responsiveness (whether or not subjects are treatment responders).

C. The specification of how to account for intercurrent events to reflect the scientific question of interest:

For this study, intercurrent events such as blood transfusion or medical treatment with prednisone or major modification in insulin regimen/doses outside the once recommended in the protocol that would render subsequent values as not protocol-meaningful will be set to missing (moved to the SDTM SUPPLB domain to facilitate sensitivity analysis that includes the values) and primary statistical methodologies of multiple imputation will be used to predict what the values were likely to be had the intercurrent event not happened.

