6.1.3 Tertiary and Exploratory Efficacy

- Standard deviation of daily CGM and associated CV%
- Plasma (non-genomic) biomarkers
- Diabetes treatment satisfaction questionnaire (s)
- Change from baseline in number of bolus injections of insulin
- An analysis of responders HbA1c < 7% without any severe hypoglycemic events, weight gain, diabetic ketoacidosis

Additionally, a quality of life (Likert Scale) question is classified as an exploratory variable of interest: At Week 12, the patient should be asked to respond to the following QOL question with one of the answers below. The answer will be entered in the EDC.

Question: “How is your quality of life relative to study start?”

Answers (choose one): markedly worse, moderately worse, slightly worse, no change, slightly improved, moderately improved, markedly improved.

The Diabetes Treatment Satisfaction Questionnaire status version (DTSQs) is completed at Screening and Week 12, and the Diabetes Treatment Satisfaction Questionnaire change version (DTSQc) is completed at the Week 12 visit. These questionnaires will be evaluated as exploratory variables of analysis in this Part.

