6.3 Pharmacokinetics Variables

Plasma trough concentrations of TTP399 will be examined as variables of analysis.

7 Statistical Methodology

Descriptive statistics will be used to summarize the data. Continuous variables will be presented showing number of observations available, mean, median, minimum, maximum, and standard deviations (or standard errors, depending on the variable) by visit. Categorical variables will be presented showing frequencies and percentages by visit.

Efficacy analyses will also be done on the FAS and, potentially, also on the PPS. If the PPS differs from the FAS by more than 10%, the analyses will be replicated on the PPS. If the PPS and the FAS do not differ by more than 10%, analysis may not be done on the PPS. Final judgments will be made at the blind data review meeting in accordance with ICH E9.

All tests will be 2-sided and use $\alpha = 0.049$ for the final analysis to accommodate planned interim analyses for which $\alpha = 0.001$ is allocated, thereby preserving a study-wise over all $\alpha = 0.05$. This penalty is applied regardless of whether or not there is an actual modification to the study structure, design, or analysis plans.

Data displays will include the following comparisons:

- **Placebo**
- **800 mg TTP399.**

MedDRA version 21.0 or later will be used. SAS version 9.4 will be used.

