7.6.2 Secondary Efficacy

All secondary endpoints will use the FAS.

Categorical endpoints will utilize Fisher's exact test.

Continuous secondary endpoints will be summarized by treatment group and visit. MMRM will also be used to analyze those endpoints.

Statistical methodology for secondary analysis will conform to methodology for primary analysis following the ITT principle and using observed-cases approach and LOCF approach using the last assessment. The Likert-scale QoL question will be dichotomized as "improved quality of life" or "no change in quality of life or worse." Fisher's exact test will be done to compare subjects treated with TTP399 with subjects treated with placebo.

Measurement variables will be analyzed using ANCOVA and ANOVA procedures, using parametric (if warranted) and nonparametric methods. Parametric assumptions will be examined; if parametric assumptions are found to be unwarranted, rank analogues will be advanced.

Secondary efficacy analysis on measures that are continuous will examine drug effects within each treatment group using:

- Paired-t test (1-sample t-test)
- Wilcoxon (1-sample) test.

Within each treatment group, the significance of the percent change from baseline will be assessed using a paired-t test (1-sample t-test). Supportive analysis will be done using a Wilcoxon (1-sample) test.

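### The protocol prints six unbalanced answers for the quality-of-life question and the SAP prints seven balanced ones; if the form follows the protocol, the mean score in Evaluation 7 has no defined scale

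*Protocol*

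**What the plan says.** Protocol 8.13 has the patient choose one answer at Week 12 from this list: "markedly worse, moderately slightly worse, no change, slightly improved, moderately improved, markedly improved". The Week 12 procedures for Part 1 (Protocol 7.2.6) and Part 2 (Protocol 7.3.10) send the site to 8.13 to ask the question and enter the answer in EDC.

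SAP 6.1.3 repeats the question with this list: "markedly worse, moderately worse, slightly worse, no change, slightly improved, moderately improved, markedly improved". It gives the answers no numeric scores. It also says that "a quality of life (Likert Scale) question is classified as an exploratory variable of interest".

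SAP Section 2, Evaluation 7, the last step listed in the conditional sequence, sets its null and alternative hypotheses on "The mean score for the single-item Likert scale for overall improvement in quality of life at Week 12".

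SAP 7.6.2 gives a different analysis: "The Likert-scale QoL question will be dichotomized as" improved on one side and unchanged or worse on the other, and Fisher's "exact test will be done to compare subjects treated with TTP399 with subjects treated with placebo".

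On precedence, Protocol Section 10 states: "The SAP will supersede the protocol for analyses".

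**The concern.** The two documents describe different response scales for one question, and the text that sites are told to use is the unbalanced one. Its second option runs moderate and slight worsening together, which is not a coherent choice for a patient.

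The SAP's precedence covers analysis. It cannot restore a distinction that was never recorded: if the form offers six options, nobody can later tell moderate from slight worsening.

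A mean score is exposed to this. With six options coded in equal steps around no change, marked improvement counts +3 and marked worsening only -2. Two arms with the same balance of better and worse answers, but different spread, could then show a mean difference that is absent on the seven-point list. A benefit made up largely of less worsening could be under-counted.

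The SAP also names two analyses for this item, a mean-score comparison and a Fisher test on a dichotomy, and only the first depends on how worsening is graded.

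**Working it through.** The documents give no power, effect size or SD for this item, so there is no design figure to reproduce.

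**Inputs from the documents.** Protocol 8.13: 6 answers (2 worse, 1 neutral, 3 improved). SAP 6.1.3: 7 answers (3, 1, 3). SAP Section 1.7: 45 per arm. SAP Section 7: "All tests will be 2-sided and use $\alpha = 0.049$ for the final analysis".

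**Assumptions.** The answer distributions, the scores and the use of a two-sample t-test for the mean are mine, for illustration only.

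**Step 1: what the merged option does to the mean.** Take a symmetric seven-point distribution with shares p1, p2, p3 at slight, moderate and marked change on each side. Its seven-point mean is 0. On the six-option list, let marked worsening score e and the merged option score m. Then

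mean = p3(3 + e) + p2(2 + m) + p1(1 + m).

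Two such patterns (p1, p2, p3), each the same on both sides:
- narrow: 0.18, 0.05, 0.02, with 0.50 unchanged
- wide: 0.15, 0.15, 0.12, with 0.16 unchanged

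| Scoring (e, m) | Mean reduces to | Narrow | Wide | Wide minus narrow |
|---|---|---|---|---|
| (a) equal steps: -2, -1 | p3 + p2 | 0.07 | 0.27 | +0.20 |
| (b) -3, -1.5 | 0.5·p2 - 0.5·p1 | -0.065 | 0.00 | +0.065 |
| (c) -3, -2 | -p1 | -0.18 | -0.15 | +0.03 |
| (d) -3, -1 | p2 | 0.05 | 0.15 | +0.10 |

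**Step 2: rejection rates.** t-test, 45 per arm, two-sided 0.049, 20,000 simulated trials, wide against narrow:

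| Scoring | Favours wide arm | Favours narrow arm |
|---|---|---|
| seven-point | 2.3% | 2.6% |
| (a) | 10.0% | 0.4% |
| (b) | 3.9% | 1.6% |
| (c) | 3.0% | 2.2% |
| (d) | 5.3% | 1.1% |

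**Step 3: is the direction general?** Put 25% on each side at moderate change in one arm and 25% on each side at marked change in the other. The second arm is more spread. From the formula, the mean goes from 0.25 to 0.25 in (a), 0.125 to 0 in (b), 0 to 0 in (c) and 0.25 to 0 in (d). Under (d) the test then rejects against the more spread arm in 9.7% of trials and for it in 0.4%. The direction is not fixed.

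**Step 4: equal distributions in both arms.** The same formula applies to each arm, so the expected difference is 0. Simulated rejection stays at about 5% under every scoring.

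**Step 5: benefit mainly through less worsening.** From markedly worse to markedly improved, placebo 5/15/20/35/15/7/3% against active 3/7/15/40/20/10/5%. The seven-point means are -0.27 and 0.17, a difference of 0.44. Under (a) they are -0.07 and 0.27, a difference of 0.34. Power (40,000 trials) is about 34% on seven points, about 29% under (a), and between 28% and 33% across (a) to (d).

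**Step 6: the Fisher test in SAP 7.6.2.** The three improved answers are identical in both lists, and every grade of worsening falls in the same category as no change. The 2×2 table is therefore the same with six or seven options. With 25% improved in both arms, exact enumeration gives 2.7% rejection, half in each direction. This shows insensitivity to the list, not to spread: in the wide-against-narrow example the improved shares are 42% and 25%, and Fisher's test favours the wide arm in 32% of trials with either list.

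**The case against.** The best reply is that this is a dropped word, not a designed six-point scale. The merged option makes no sense as written, the SAP prints all seven answers, and the SAP governs the analysis. The EDC pick-list is not in the documents, so nothing shows that a patient was ever offered six options. The one test that the SAP specifies for this item by name is unaffected. All of that stands, and it keeps the impact low. It does not remove the need to correct text that both Week 12 procedures point to, or to check the form.

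A reader might infer something stronger: that the unbalanced list would make Evaluation 7 favour the arm with more spread answers, or would inflate its type I error. The documents do not support that. Neither assigns scores, so the effect rests on an assumed equal-step coding and on arms that differ in spread. Under other codings it shrinks, and it can reverse (step 3). When the arms share one distribution there is no inflation (step 4). Nor does anything in the documents suggest that TTP399 would widen the answers symmetrically.

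**Conclusion.** The discrepancy is real and sits in operational text: six answers in Protocol 8.13, seven in SAP 6.1.3. If the form follows 8.13, the seven-level item is lost and Evaluation 7's mean has no defined, balanced scale. Under equal-step scoring the mean difference could be distorted, by +0.20 in the illustration, with rejection of 10.0% against 0.4%. Both size and direction depend on unstated scores and assumed answer patterns, so no single bias figure should be attached to this trial.

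The impact is low. The item is classed as exploratory, Evaluation 7 is the last step listed so no later test depends on it, and the dichotomy in SAP 7.6.2 does not change with the list. The conflict inside the SAP, a mean score in Evaluation 7 against a dichotomy in 7.6.2, would remain even with the protocol corrected and should be settled at the same time.

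**What to change.** 1. Correct Protocol 8.13 to the seven answers in SAP 6.1.3.
2. Check which list the EDC pick-list offers, and correct it if it has six.
3. Make Evaluation 7 and SAP 7.6.2 name the same analysis. If a mean is kept, state the scores (-3 to +3) and the test. If the dichotomy is kept, reword the Evaluation 7 hypotheses as proportions improved.
4. Analyse any answers already collected on six options with the improved versus not-improved dichotomy in 7.6.2, where the merged option does no harm.

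The cost is one line in the protocol, one check of the form, and a sentence or two in the SAP before unblinding.

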9. ADVERSE EVENTS REPORTING

9.1. Adverse Events

An AE is any untoward medical occurrence in a clinical study participant administered a pharmaceutical product. Study drug treatment does not necessarily have a causal relationship with the AE. An AE, therefore, can be any unfavorable change in structure, function, or chemistry (including abnormal clinical laboratory, vital signs, or ECG findings), symptoms, signs, or diseases temporally associated with the use of a medicinal (investigational) product, whether or not related to the medicinal (investigational) product, as defined by ICH.

The criteria for determining whether an abnormal objective test finding should be reported as an adverse event are as follows:

- Test result is associated with accompanying symptoms, and/or
- Test result requires additional diagnostic testing or medical/surgical intervention, and/or
- Test result leads to a change in study dosing or discontinuation from the study, significant additional concomitant drug treatment, or other therapy, and/or

Test result is considered to be an adverse event by the Investigator or Sponsor.

Merely repeating an abnormal test, in the absence of any of the above conditions, does not constitute an adverse event. Any abnormal test result that is determined to be an error does not require reporting as an adverse event.

